### 7.3.2 Treatment Discontinuation

After treatment assignment, a subject may stop treatment permanently for a variety of reasons. Treatment discontinuations may be initiated by a subject who is not satisfied with treatment or may become medically necessary due to AEs, required treatment with a disallowed medication or therapy, or other issues, as determined by the investigator.

However, each investigator must comprehensively review the circumstances and offer the subject options for continued treatment to the degree possible. If, after discussion with the investigator about possible mitigations for AEs, etc., the subject still chooses to discontinue IMP, the subject will permanently discontinue IMP and will complete the ET Visit assessments and will complete the Safety Follow-Up Visit, 4 weeks after last dose of IMP and the subject will not be allowed to re-start the IMP.

Trial medication is to be permanently discontinued if ESA rescue (other than darbepoetin alfa in comparator arm, any ESA in vadadustat arm) is not in the setting of acute bleeding (ie, gastrointestinal bleed, surgery, excess bleeding) and one of the following:

- The first cycle of ESA rescue lasts >30 days or
- Subject requires a second cycle of ESA for rescue (that must be related to anemia) at any time.

Trial medication must be permanently discontinued if a subject meets one of the criteria in [Table 7.3.2-1](#).

Table 7.3.2-1 Trial Medication Stopping Rules	
ALT or AST > 3x ULN and total bilirubin > 2x ULN	Permanently Discontinue Treatment
ALT or AST > 3x ULN and INR > 1.5	Permanently Discontinue Treatment
ALT or AST > 8x ULN	Permanently Discontinue Treatment
ALT or AST remains > 5x ULN over 2 weeks a	Permanently Discontinue Treatment
ALT or AST > 3x ULN with symptoms including eg, fatigue, nausea, vomiting, right upper quadrant pain, fever, rash or eosinophilia	Permanently Discontinue Treatment

INR: international normalized ratio; ULN: upper limit of normal

aRe-challenge generally should be avoided with ALT or AST > 5x ULN unless there are no other good therapeutic options.

See [Section 8.8](#) for reporting requirements related to a subject being permanently discontinued based on meeting the laboratory abnormalities list above in [Table 7.3.2-1](#).

For subjects who permanently discontinue IMP, the investigator will resume standard of care treatment, including ESAs and iron therapy, as deemed appropriate.

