## **9.3 Handling of Missing Data for Primary and Secondary Endpoint Analysis**

It is expected that up to 30% of subjects will discontinue the trial. The reasons for discontinuation will be summarized by treatment arm. Missing Hb values will be imputed using multiple imputation.

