##### **9.4.2.1 Adverse Events**

Adverse events will be summarized using the number and percentage of subjects with AEs for all subjects in the safety population. Summaries will also be provided for subgroups including Region, Age, Gender, and Race.

All AEs will be coded using Medical Dictionary for Regulatory Activities (MedDRA). Treatment-emergent and post-treatment AEs will be summarized by SOC and preferred term for each treatment group. Adverse events will also be summarized by their maximum severity.

Summaries will also be provided for the following types of AEs:

- SAEs.
- Related AEs (including all categories for relationship to IMP other than “Unrelated”, as determined by the investigator).
- AEs leading to early discontinuation of IMP.
- Summaries on adjudicated events (see [Section 9.5](#)) will be provided by treatment group.

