10.3 Adverse Events and Serious Adverse Events

The AE eCRF has been designed to capture all events from time of signing the informed consent through the Safety Follow-up visit. Subjects must be followed for AEs until the final required protocol visit or until all drug-related toxicities and serious adverse events (SAEs) have resolved (or are considered chronic/stable), whichever is later. All AEs will be coded by Medical Dictionary for Regulatory Activities (MedDRA) system organ class (SOC) and preferred term (PT). The MedDRA version used for reporting this study will be described in a footnote on AE related outputs.

Treatment-emergent AEs (TEAEs) are defined as AEs with an onset date on or after the start of IMP treatment. In more detail, TEAEs are all adverse events which started after start of IMP treatment; or if the event was continuous from baseline and was worsening, serious, IMP related, or resulted in death, discontinuation, interruption or reduction of IMP.

All TEAE summaries will provide the number of subjects reporting at least 1 TEAE. Tables will present the number and percentage of subjects by treatment group reporting at least 1 of the following:

- TEAE, SOC, and PT
 - TEAE leading to withdrawal of study medication, SOC, and PT
 - TEAE, severity, SOC and PT
 - Drug-related TEAE, SOC, and PT
 - Drug-related TEAE leading to withdrawal of study medication, SOC, and PT
- Treatment-emergent SAE, SOC, and PT
 - Drug-related treatment-emergent SAE, SOC, and PT
 - Fatal TEAE, SOC and PT.

A summary table will show number of subjects with at least 1 of each of the following:

- AE,
- SAE,
- TEAE,
- Severe TEAE
- TEAE leading to withdrawal of study treatment,

- Drug-related TEAE leading to withdrawal of study treatment,
- Drug-related TEAE,
- Treatment-emergent SAE,
- Drug-related treatment-emergent SAE,
- Fatal TEAE,
- All death.

TEAEs reported at least 5% of subjects in any treatment groups, and non-serious TEAEs reported at least 5% of subjects in any treatment groups will be summarized by SOC and PT for each treatment group.

TEAEs will be summarized by 1) worst severity, and 2) worst causality by SOC and PT. For each subject and each PT, the worst severity recorded will be used in the by-severity summaries. Similarly, the most conservative causality assessment (most related to treatment) will be attributed and used in the by-causality summaries. If severity or causality is missing, data will be imputed to the worst category.

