A by-subject listing of all AEs will be provided. This listing will be presented by treatment group and will include center, subject identifier, age, sex, race, AE (SOC, PT, and verbatim term), flag of TEAE, study day of onset, study day of resolution, duration, severity, seriousness, relationship to the study medication, action taken, outcome and causality.

AEs of special interest (AESI) listed in [Appendix D](#) will be summarized by treatment group. The number and percentage of subjects reporting these AESI will be provided.

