10.4 Major Adverse Cardiovascular Event (MACE)

Potential safety events will be collected in Safety Event Data Collection eCRF page. The occurrence of any potential safety events will be summarized by SOC and PT for each treatment group, and a by-subject listing will be provided.

An independent Safety Event Adjudication Committee (SEAC) that is composed of independent experts will be formed prior to trial commencement to adjudicate the MACE (all-cause mortality, non-fatal myocardial infarction (MI), and non-fatal stroke) plus hospitalization for heart failure (HF) or thromboembolic event excluding vascular access thrombosis. Adjudicated safety events will be summarized for each treatment group, and a by-subject listing will be provided.

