Section 9.4.5 (Receipt of ESA Rescue)	
Clarified that ESA rescue medications include narrow or broad-on-treatment therapies with $\geq 50\%$ or $\geq 100\%$ dose increase in darbepoetin alfa.
 
Clarified that Mantel-Haenszel method will be used for estimation of risk difference.
 
Added time to first ESA rescue analyses.

Section 9.4.6 (Proportion of Subjects Receiving Red Blood Cell (RBC) Transfusions)	
Clarified that RBC transfusions include narrow or broad-on-treatment.
 
Clarified that Mantel-Haenszel method will be used for estimation of risk difference.
 
Added time to first RBC transfusion analyses.

Section 9.5 (Study Level Type I Error Control)	Added a section of study level type I error control.

Section 10.2 (Hb-related Safety Endpoints)	Clarified that calculation of number and proportion of subjects in Hb-related safety endpoints.
Section 10.3 (Adverse Events and Serious Adverse Events)	
Clarified that AE will be coded by SOC and PT, and MedDRA version will be shown in AE outputs.
 
Clarified the definition of TEAE.
 
Added AE, SAE and all death in the summary table.
 
Removed the AE summary order statement.
 
Clarified the most conservative causality AE assessment will be used in the by-causality summaries.
 
Changed TEAE listing to AE listing and added a flag of TEAE in AE listing.

Section 10.4 (Major Adverse Cardiovascular Event)	
Added “excluding vascular access thrombosis” to the “thromboembolic event”.
 
Removed “by SOC and PT” from the summary of adjudicated safety events.
 
Remove time to the first occurrence of MACE analyses.

Section 10.5.1 (Clinical Laboratory Evaluation)	
Removed “by analysis period” from the summary of liver function abnormalities.
 
Changed “versions of Hy’s Law” to “laboratory values fulfilling potential liver injury criteria”.
 
Removed summary and shift from baseline of abnormal laboratory values in CTCAE grade.
 
Removed summary of additional laboratory parameters listed in Appendix, and removed the corresponding Appendix.

Section 10.5.2 (Vital Signs, ECGs, and Physical Findings)	
Clarified the calculation of percentage of subjects experiencing findings.
 
Added “QTc interval” criteria.
 
Removed “at baseline” from the ECG summary.
 
Removed summary of potential clinical relevance listed in Appendix, and removed the corresponding Appendix.

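### Adverse events are summarised as crude percentages, and deaths and adjudicated MACE as by-arm summaries, with no measure that accounts for follow-up time, which may differ by arm

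*SAP*

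**What the plan says.** **How events are summarised.** Protocol 9.4.2.1: "Adverse events will be summarized using the number and percentage of subjects with AEs for all subjects in the safety population". SAP 10.3: "All TEAE summaries will provide the number of subjects reporting at least 1 TEAE", and "Tables will present the number and percentage of subjects by treatment group reporting at least 1 of the following", followed by TEAEs, treatment-emergent SAEs, drug-related and fatal events. For AESIs: "The number and percentage of subjects reporting these AESI will be provided". SAP 10.1 reports number and cause of death by arm. SAP 10.4: "Adjudicated safety events will be summarized for each treatment group, and a by-subject listing will be provided".

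**What is absent.** The visible SAP text and the Section 19 output list contain no person-time rate, cumulative incidence or hazard ratio for AEs, deaths or MACE. The revision table (SAP Section 20, row for Section 10.4) confirms that the absence is deliberate for MACE: "Remove time to the first occurrence of MACE analyses". Duration of exposure to study treatment has its own tables (14.1.9.6.1 and 14.1.9.6.2) but is not linked to event counts.

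**How follow-up ends.** AEs are collected from consent to the Safety Follow-up Visit (protocol 8.8.2.1). A subject who stops treatment permanently has the ET Visit and then that visit, about 4 weeks later (protocol 7.3, 7.3.2). Protocol 9.3: "It is expected that up to 30% of subjects will discontinue the trial". No split by arm is given.

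**The rule that differs by arm.** Protocol 7.3.2: "Trial medication is to be permanently discontinued if ESA rescue (other than darbepoetin alfa in comparator arm, any ESA in vadadustat arm"). It applies outside acute bleeding, when the first rescue cycle exceeds 30 days or a second anaemia-related cycle is needed.

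**The concern.** A percentage of subjects with at least one event depends on the event rate and on how long subjects are watched. If one arm is watched for less time, its percentage falls even when the underlying rates are equal.

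Here one route out of the trial is worded differently by arm. A vadadustat subject whose haemoglobin falls and who needs prolonged or repeated ESA rescue must stop. In the control arm the study drug is itself an ESA, and SAP 6.4 accepts that a dose increase may be planned titration. Stopping treatment then closes the AE window about 4 weeks later. The background gives some reason to take this seriously: protocol 4.3 reports that six of 31 subjects on TIW dosing in the phase 2 haemodialysis trial were withdrawn for worsening anaemia, although this trial uses higher TIW doses to counter that.

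Showing safety is part of the primary objective (SAP 2.4), so readers will set these percentages side by side. The SAP already handles time for other outcomes: Cox and Kaplan-Meier analyses for rescue and transfusion (6.4, 9.4.5, 9.4.6), and per-period denominators of subjects with data for Hb and vital-sign abnormalities (10.2, 10.5.2).

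**Working it through.** The plan states no AE or MACE rate, count or precision, so it has no figure of its own to reproduce on this point. What follows is an illustration.

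**Inputs from the documents.** 1:1:1 allocation; 52 weeks of treatment plus 4 weeks of safety follow-up; up to 30% discontinuation overall.

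**Assumptions.** The same constant hazard λ (first events per person-year) in every arm; exponential dropout with proportion q leaving by Week 52; AE follow-up = min(dropout time, 52) + 4 weeks; overall dropout held at 30%. For example, (20% + 35% + 35%)/3 = 30%.

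**Formulas.** Let a = −ln(1 − q).

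- Mean follow-up in weeks = 4 + 52q/a
- Crude proportion P = 1 − e^(−4λ/52) × [a/(a+λ) × (1 − e^(−(a+λ))) + e^(−(a+λ))]

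**Worked case, 20% versus 35%, λ = 0.2.**

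- Darbepoetin alfa: a = 0.2231. Mean follow-up = 4 + 52 × 0.20/0.2231 = 50.6 weeks. P = 1 − 0.9847 × (0.5273 × 0.3450 + 0.6550) = 17.6%.
- Each vadadustat arm: a = 0.4308. Mean follow-up = 4 + 52 × 0.35/0.4308 = 46.2 weeks. P = 1 − 0.9847 × (0.6829 × 0.4678 + 0.5322) = 16.1%.

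**Range** (darbepoetin alfa / each vadadustat arm; gaps are taken from unrounded values):

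| Dropout | Mean follow-up, weeks | Crude %, λ = 0.2 | Gap | Crude %, λ = 1.0 | Gap |
|---|---|---|---|---|---|
| 30% / 30% | 47.7 / 47.7 | 16.6 / 16.6 | 0.0 | 58.1 / 58.1 | 0.0 |
| 25% / 32.5% | 49.2 / 47.0 | 17.1 / 16.4 | 0.7 | 59.5 / 57.4 | 2.1 |
| 20% / 35% | 50.6 / 46.2 | 17.6 / 16.1 | 1.5 | 60.8 / 56.6 | 4.2 |
| 10% / 40% | 53.4 / 44.7 | 18.5 / 15.6 | 2.9 | 63.4 / 55.2 | 8.3 |

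Put the other way round, in the 20% / 35% case a true hazard ratio of about 1.10 (λ = 0.2) to 1.13 (λ = 1.0) against vadadustat would show as equal percentages.

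**Person-time rate.** Under a constant hazard, expected first events equal λ times expected person-time at risk. The rate ratio is therefore 1.00 in every row.

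**The case against.** **Unequal follow-up is not established.** A reader might infer from protocol 7.3.2 that vadadustat subjects will be followed for less time and so will look safer. The documents do not show that. The trigger is narrow, and an ESA other than the study drug triggers it in the control arm too. The remaining exits (AE, lack of efficacy, transplant, change of dialysis modality, the 30-day interruption limit) apply to all arms. This objection stands: the direction is plausible, not proven.

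**A larger gap is easy to construct but does not fit the plan.** With mean follow-up of 0.75 versus 0.90 year and λ = 1.0, 1 − e^(−0.75) = 52.8% and 1 − e^(−0.90) = 59.3%, a gap of 6.6 points. Under the follow-up model above, those means need about 57% and 33% dropout, or (57 + 57 + 33)/3 = 49% overall, against the stated maximum of 30%.

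**The gap is small against sampling error.** With 100 per arm, the 95% half-width for 60.8% versus 56.6% is 1.96 × √(0.608 × 0.392/100 + 0.566 × 0.434/100) = 13.6 points. SAP Section 10 makes most safety analysis descriptive. Both points are true, but a systematic shift does not disappear because it is smaller than the noise, and side-by-side reading is exactly what these tables are for.

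**Rates have their own bias.** Suppose 30% of each arm has a first event at Week 4 and none later, with mean follow-up of 46.2 versus 50.6 weeks. The percentages are correctly equal. The rates are 0.30/(0.30 × 4/52 + 0.70 × 46.2/52) = 46.5 and 0.30/(0.30 × 4/52 + 0.70 × 50.6/52) = 42.6 per 100 patient-years, a false 9% excess on vadadustat. This stands, and it is why rates should not replace percentages.

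**Some information is already planned.** Treatment exposure, reasons for discontinuation by arm and AE onset day will all be reported, and an unblinded IDMC reviews safety. A reader could see that exposure differs, but could not correct for it from the planned tables.

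**Conclusion.** The point holds as a gap in reporting. TEAEs, SAEs and AESIs are planned only as numbers and percentages of subjects. Deaths and adjudicated MACE are planned only as by-arm summaries; the SAP names no denominator in 10.1 or 10.4, so it would go too far to say that every one of these is defined as a crude percentage. No visible output accounts for follow-up time, and one discontinuation rule that shortens AE collection differs by arm.

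The size is modest and conditional. It is zero with equal dropout. With a 20% versus 35% split it is about 1.5 points at 0.2 events per person-year and 4.2 points at 1.0, in favour of vadadustat. These figures rest on assumed hazards that are constant and equal, and on an assumed split by arm. Because no formal AE comparison is planned, what is at stake is interpretation, not a test result. The documents do not support a claim that the safety comparison will be biased, only that the planned tables could not reveal or adjust for such a bias if it arose. Adding the measure is a cheap improvement.

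**What to change.** Keep the number and percentage of subjects. For overall TEAEs, SAEs, AESIs, deaths and adjudicated MACE, add to the SAP:

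- subjects with a first event per 100 patient-years, with 95% CI, by arm. Person-time runs from first dose to the earlier of first event or end of AE collection, and only events inside that window are counted;
- AE follow-up time by arm, shown with those tables;
- a sentence saying that the two measures are read together and that neither alone carries a between-arm statement.

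**Cost.** No new data and no change to trial conduct. A new person-time derivation is needed for each event category, because the planned exposure tables cover time on treatment only, not time to first event or to the end of AE collection. The rates assume a roughly constant hazard, can mislead if events cluster soon after conversion, and do not remove bias from informative dropout. The SAP should state these limits. The discontinuation rule itself is not at issue here.

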10.4 Major Adverse Cardiovascular Event (MACE)

Potential safety events will be collected in Safety Event Data Collection eCRF page. The occurrence of any potential safety events will be summarized by SOC and PT for each treatment group, and a by-subject listing will be provided.

An independent Safety Event Adjudication Committee (SEAC) that is composed of independent experts will be formed prior to trial commencement to adjudicate the MACE (all-cause mortality, non-fatal myocardial infarction (MI), and non-fatal stroke) plus hospitalization for heart failure (HF) or thromboembolic event excluding vascular access thrombosis. Adjudicated safety events will be summarized for each treatment group, and a by-subject listing will be provided.

10.5 Other Safety Endpoints

Observed values of continuous and categorical parameters and changes from baseline for continuous parameters to each trial visit will be summarized descriptively for vital signs and clinical laboratory results. Graphical displays of selected laboratory parameters will also be provided.

10.5.1 Clinical Laboratory Evaluation

Observed values and changes (absolute and percent) from baseline in continuous clinical laboratory results will be summarized by visit and by treatment group. If the central laboratory uses assays that have lower limits of detection (LLD), all laboratory results below the LLD will be imputed with the LLD. Results reported as greater than a value (i.e., “> value”) will be imputed as $1.5 \times$ that value.

A summary of liver function abnormalities will be provided by treatment group. Any subject with at least 1 of the following liver function abnormalities will be summarized:

- Alanine aminotransferase (ALT):
 - $>2 \times$ and $\leq 3 \times$ upper limit of normal (ULN).
 - $>3 \times$ and $\leq 5 \times$ ULN.
 - $>5 \times$ and $\leq 10 \times$ ULN.
 - $>10 \times$ ULN.
- Aspartate aminotransferase (AST):
 - $>2 \times$ and $\leq 3 \times$ ULN.
 - $>3 \times$ and $\leq 5 \times$ ULN.
 - $>5 \times$ and $\leq 10 \times$ ULN.
 - $>10 \times$ ULN.
- Total bilirubin:
 - $>2 \times$ and $\leq 3 \times$ ULN.
 - $>3 \times$ ULN.

The occurrence of events that satisfy the following laboratory values fulfilling potential liver injury criteria will be summarized. For each subject, the worse laboratory results will be considered.

- (ALT or AST $>3 \times$ ULN and $\leq 5 \times$ ULN) and total bilirubin $>2 \times$ ULN.
- (ALT or AST $>5 \times$ ULN and $\leq 10 \times$ ULN) and total bilirubin $>2 \times$ ULN.
- ALT or AST $>10 \times$ ULN and total bilirubin $>2 \times$ ULN.

The number and percentage of subjects experiencing clinically significant values for Potassium >6.0 mmol/L will be presented by analysis time period.

10 of 10

Black box

— 10 —

1

1

1

11. **What is the primary purpose of the study?** (check all that apply)

© 2019 Pearson Education, Inc.

For more information, contact the Office of the Vice President for Research and Economic Development at [contact] or [contact].

A 20x20 grid of black and white squares. The grid is mostly white with black vertical and horizontal lines. There are several black rectangular blocks of varying sizes scattered across the grid. Notable clusters of black squares are located in the top-left, middle-left, and bottom-right areas.

17 Appendix D Adverse Event of Special Interest

The list of adverse events of special interest (AESI) in the following is from Vadadustat Adverse Events of Special Interest Version 2 Final.

- Worsening of Hypertension: Hypertension MedDRA SMQ Narrow.
- Hepatotoxicity: Drug related hepatic disorders Comprehensive SMQ.
- Pulmonary Hypertension: Pulmonary Hypertension SMQ Narrow.
- Adrenal disorder: MedDRA HLGT Adrenal gland disorders and the MedDRA HLT Adrenal cortex tests.
- Malignancies including renal cell carcinoma: Malignant or unspecified tumors (SMQ) Broad.
- Congestive heart failure: Cardiac failure MedDRA SMQ Narrow.

Adverse event preferred terms used in key queries from Food and Drug Administration (FDA) [FDA, 2021a] are listed below.

- Thrombosis (FDA):

Cerebral infarction
Embolic cerebral infarction
Ischaemic stroke
Cerebellar infarction
Lacunar stroke
Embolic stroke
Brain stem stroke
Lacunar infarction
Thrombosis in device
Arteriovenous fistula thrombosis
Arteriovenous graft thrombosis
Vascular access site thrombosis
Vascular graft thrombosis
Graft thrombosis
Shunt thrombosis
Acute myocardial infarction
Myocardial infarction
Deep vein thrombosis
Thrombosis
Atrial thrombosis
Peripheral artery thrombosis
Subclavian vein thrombosis
Brachiocephalic vein thrombosis
Subclavian artery thrombosis
Vena cava thrombosis
Thrombophlebitis superficial

Arterial thrombosis
Thrombophlebitis
Jugular vein thrombosis
Venous thrombosis
Pelvic venous thrombosis
Venous thrombosis limb
Cardiac ventricular thrombosis
Intracardiac thrombus

- Device/shunt thrombosis/occlusion/malfunction/Stenosis (FDA):

Thrombosis in device
Arteriovenous fistula thrombosis
Arteriovenous graft thrombosis
Vascular access site thrombosis
Vascular graft thrombosis
Medical device site thrombosis
Device occlusion
Arteriovenous fistula occlusion
Vascular access site occlusion
Vascular access complication
Vascular access malfunction
Arteriovenous graft site stenosis
Shunt occlusion
Shunt malfunction
Vascular graft stenosis
Anastomotic stenosis
Vascular access site complication
Vascular graft occlusion

- Device/shunt thrombosis (FDA):

Thrombosis in device
Arteriovenous fistula thrombosis
Arteriovenous graft thrombosis
Vascular access site thrombosis
Vascular graft thrombosis
Graft thrombosis
Shunt thrombosis
Medical device site thrombosis
Device related thrombosis
Injection site thrombosis

- Seizure (FDA):

Epilepsy
Epileptic encephalopathy
Seizure
Generalised tonic-clonic seizure
Idiopathic partial epilepsy
Partial seizures
Tonic convulsion

- Stroke (FDA):

Cerebral infarction
Embolic cerebral infarction
Ischaemic stroke
Cerebellar infarction
Lacunar stroke
Embolic stroke
Brain stem stroke
Lacunar infarction

Cerebrovascular accident
Haemorrhagic stroke
Brain stem haemorrhage

- Sepsis/septic shock (FDA):

Device related sepsis
Enterococcal sepsis
Sepsis
Urosepsis
Streptococcal sepsis
Pseudomonal sepsis
Staphylococcal sepsis
Septic shock
Sepsis syndrome
Biliary sepsis
Bacterial sepsis
Fungal sepsis
Citrobacter sepsis
Listeria sepsis
Abdominal sepsis
Septic encephalopathy
Escherichia sepsis

18 References

Food and Drug Administration. Briefing Document. Cardiovascular and Renal Drugs Advisory Committee Meeting 2021a. Roxadustat. Table 34. Available at: <https://www.fda.gov/media/150728/download>.

